### **13.2 Randomization/Stratification**

Participants will be assigned a randomization number once the following has been accomplished: eligibility has been verified at the site level, eligibility has been confirmed by the site PI, and eligibility CRF has been entered into the DMI web application. The randomization number will be generated by the database and assigned to the participant.

A total of 48 eligible participants will be randomized 2:1 to vaccine and GM-CSF alone groups. Accounting for approx. 10% attrition rate and approx. 5% non-evaluable sample rate, we expect to achieve 40 evaluable participants, 27 in vaccination and 13 in GM-CSF alone group. We will stratify the randomization by site using random permuted block design with the block size of 6.

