## 6.5 Agent Accountability

The Investigator, or a responsible party designated by the Investigator, must maintain a careful record of the inventory and disposition of all agents received from DCP using the NCI Drug Accountability Record Form (DARF) or an institutionally-approved accountability system. The Investigator is required to maintain adequate records of receipt, dispensing and final disposition of study agent. Include on receipt record from whom the agent was received and to whom study agent was shipped, date, quantity and batch or lot number. On dispensing record, note quantities and dates study agent was dispensed and administered to each participant. Drs. [name] or [name], [name] and [name] or their representatives will be responsible for study agent accountability for participants at Dana-Farber Cancer Center, UT MD Anderson Cancer Center, and Thomas Jefferson University, respectively.

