## **6.9 Blinding and Unblinding Methods**

- 6.9.1 Participants will be blinded to NeuVax™ or GM-CSF alone arm assignment.
- 6.9.2 The Statistician, Site Study Pharmacist and other investigators will not be blinded to NeuVax™ or GM-CSF alone arm assignment.
- 6.9.3 Participants randomized to the nelipepimut-S/GM-CSF arm will receive two vaccinations of nelipepimut-S (1000 µg) and GM-CSF (250 µg) consisting of 4 intradermal inoculations two weeks apart prior to surgery. Participants randomized to the GM-CSF alone arm will receive inoculations of GM-CSF (250 µg) administered in an identical manner to those receiving nelipepimut-S/GM-CSF.
- 6.9.4 At the end of the study participants will be unblinded to their assignment.
- 6.9.5 Study agents may be unblinded during the course of the study if deemed medically necessary in the event of a serious adverse event after discussion with the NCI medical monitor. Unblinding will be conducted as follows:
  - 1) The Site PI contacts the Protocol Principal Investigator ([name], PhD) and requests the participant’s treatment status be unblinded.
  - 2) The Protocol Principal Investigator ([name], PhD) contacts the NCI DCP Medical Monitor ([name], MD) and requests the participant’s treatment status be unblinded. The Protocol Principal Investigator then conveys the Medical Monitor’s decision to the Site PI. The Site PI then proceeds with unblinding as written out below.
  - 3) If the NCI Medical Monitor cannot be reached and the participant requires emergency care, the Protocol Principal Investigator ([name]) may authorize the site PI to break the blind.
  - 4) If the Site PI is unable to reach the Protocol Principal Investigator and the participant requires emergency care, then the Site PI must proceed with unblinding as written out below.
  - 5) The Site PI officially unblinds the participant and takes the participant off-study.
  - 6) The date and reason for breaking the blind must be submitted by the Site PI to the Protocol Principal Investigator, [name], PhD as soon as possible.

- 7) It is the responsibility of the Protocol Principal Investigator to report the date and reason for breaking the blind to the NCI Medical Monitor, [name], MD as soon as possible after receiving this information from the Site PI.

NCI Medical Monitor:  
[name], MD  
NCI/Division of Cancer Prevention  
[name]  
[name]  
[name]  

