### **13.3 Accrual and Feasibility**

We plan to consent and screen 108 potentially eligible subjects in the study over 2.5 years at four clinical centers. Our goal is to randomize 48 participants. The randomized participants will receive the intervention for approx. 4 weeks; and will be followed up for an additional approx. 3-6 months period. They will be followed closely to monitor the toxicity and drug compliance.

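### One printed block size of 6 within site, with unblinded investigators, would let anyone tracking a site's earlier assignments deduce about a quarter of them before entry

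*Combined protocol and SAP*

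**What the plan says.** Section 13.2 sets the ratio and the method: "A total of 48 eligible participants will be randomized 2:1 to vaccine and GM-CSF alone groups", and then "We will stratify the randomization by site using random permuted block design with the block size of 6". No other size is mentioned, so each block within a site has 4 vaccine and 2 control places.

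Section 6.9.1 masks the participants. Section 6.9.2 reads: "The Statistician, Site Study Pharmacist and other investigators will not be blinded to NeuVax™ or GM-CSF alone arm assignment". Under Sections 6.8 and 13.2 the database issues a number only after the site PI has confirmed eligibility and the eligibility form has been entered.

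Section 6.9.5 points the other way on what a Site PI knows. It has the Site PI ask for a participant's arm to be revealed, and then: "The Site PI officially unblinds the participant and takes the participant off-study".

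Section 13.3 plans accrual "over 2.5 years at four clinical centers". Section 6.5 lists three institutions for agent accountability: "Dana-Farber Cancer Center, UT MD Anderson Cancer Center, and Thomas Jefferson University, respectively". Expected accrual per site is not given. Section 10.2 masks the laboratories to participant identity and visit.

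The plan describes neither varying block sizes nor any limit on which site staff may see earlier assignments before the next woman is randomized.

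**The concern.** Issuing the number centrally, after eligibility is confirmed, hides the list. It does not hide the end of a block from someone who knows the block size and has seen the earlier assignments at that site. Here the size is printed in the protocol that each site's investigators hold, 6.9.2 lets investigators know past assignments, and the site PI is also the gatekeeper for entry.

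What is at stake is selection at entry. Some entry criteria rest on judgement: Section 4.2.6 turns on the investigator's opinion about safety, and Section 4.2.14 on psychiatric or social circumstances that would limit compliance. Compliance bears on the primary comparison, because Section 5.7 counts a woman as evaluable only if she completes the pre-surgical vaccinations and the one-month visit, and Section 13.6 excludes missing primary data. About 13 evaluable controls are expected, so a few steered entries could matter. A masked assay guards against biased reading, not against selection.

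**Working it through.** The documents state no figure for predictability, so there is none to reproduce. (The plan's 82% power for 27 against 13 does reproduce, at 82.3% by the two-sided t-test, and is not in question.)

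**Inputs.** Block of 6, stratified by site, 2:1, 48 women (13.2); four sites (13.3), or three if the list in 6.5 is complete. Accrual per site is an assumption throughout.

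**Step 1: one complete block.** There are C(6,2) = 15 equally likely orderings. An assignment is certain when one arm's places in the block are already used up. The best guess names the arm with more places left.

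| Position | Certain vaccine (of 15) | Certain control (of 15) | Certain in all (of 15) | Best guess right (expected, of 15) |
|---|---|---|---|---|
| 1 | 0 | 0 | 0 | 10 |
| 2 | 0 | 0 | 0 | 10 |
| 3 | 1 | 0 | 1 | 10 |
| 4 | 3 | 0 | 3 | 11 |
| 5 | 6 | 1 | 7 | 11 |
| 6 | 10 | 5 | 15 | 15 |
| Sum | 20 | 6 | 26 | 67 |

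- Certain: 26/90 = 28.9%, or 26/15 = 1.733 per block. Closed form: 4/(2+1) + 2/(4+1) = 1.333 + 0.4 = 1.733.
- Of these, 20/26 = 77% are vaccine. Certain controls are 6/90 = 6.7% of all assignments.
- Best guess right: 67/90 = 74.4%. Always naming vaccine is right 4/6 = 66.7% of the time.

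**Step 2: the whole trial, with incomplete last blocks.** A site with n women has an expected floor(n/6) × 26/15 + c certain assignments. For a remainder of 0 to 5 women, c = 0, 0, 0, 1/15, 4/15, 11/15.

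- 12, 12, 12, 12: 4 × 52/15 = 13.87 of 48 = 28.9%, the maximum.
- 11, 11, 13, 13: 2 × (37 + 52)/15 = 11.87 of 48 = 24.7%.
- 9, 15, 9, 15: 2 × (27 + 53)/15 = 10.67 of 48 = 22.2%, the minimum over all four-site splits.

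With 48 women falling at random over four sites of equal rate (20,000 simulated splits), the mean is 24.3% and 37% of splits exceed 25%. With unequal rates drawn at random, the mean is 24.6% and 47% exceed 25%. With three sites the range is 23.3% to 28.9%, and the mean is 25.5% at equal rates.

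**Step 3: varying block sizes.** A site of 12 women was simulated with a guesser who sees every earlier assignment and knows which sizes are possible, but not which one is in use. The certain share was 28.9% for fixed 6, 5.3% for sizes 6 and 9, and 2.8% for sizes 3, 6 and 9; other runs gave up to 5.7% and 2.9%. Twelve per site is the split at which fixed blocks of 6 fill exactly, so it shows the fixed design at its worst. The gain comes from varying and hiding the size, not from smaller blocks: a known fixed block of 3 would leave 44.4% certain, and a known fixed block of 9 would leave 21.4%.

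**The case against.** A fair defence has several parts.

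- *The usable information is modest.* Most certain assignments are to the arm already favoured 2:1. The best guess gains only 7/90 = 7.8 percentage points over always naming vaccine, and the first two places in a block are never certain. This stands.
- *Nobody is shown to keep a running list.* The documents do not say that enrolling staff see one, and a Site PI who must request unblinding under 6.9.5 fits poorly with one who already knows every arm. This stands as a limit on how far the point goes. It does not remove the point, because 6.9.2 permits the knowledge and nothing restricts it.
- *Holding a woman back for a preferred place is hard.* Section 3 expects 1 to 2 women a month overall. Spread evenly over four sites (an assumption), that is one per site every 2 to 4 months, while baseline evaluation must fall within 30 days before randomization. This largely stands. Declining or discouraging an entry remains possible, and slow accrual also makes the sequence easy to follow.

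A reader might also infer that sites could select on baseline CTL, HER2 level or tolerance of vaccination. The documents do not support that. Baseline CTL blood is drawn at Vaccination #1, after randomization. Section 13.9 treats HER2 testing at baseline as something a re-design would add, so no HER2 result is required before randomization. Tolerance cannot be seen at entry. Any selection would act through what is visible at screening.

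**Conclusion.** The weakness is real and of moderate size. Someone at a site who tracks earlier assignments could deduce about a quarter of them in advance: 28.9% in complete blocks, and an expected 22% to 29% (10.7 to 13.9 of 48 women) at four sites. This rests on the printed block size, on investigators seeing past assignments as 6.9.2 allows, and on accrual per site that the documents do not give.

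Two stronger readings should be resisted. One is that over a quarter of assignments are known in advance: at four sites of equal rate the share exceeds 25% in only 37% of simulated splits, and deducible is not the same as known. The other is that concealment is lost or the comparison biased: concealment is weakened, and no passage shows that anyone has used the information.

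**What to change.** In Section 13.2, replace the fixed size with randomly varying block sizes in multiples of 3 (for example 3, 6 and 9) for blocks not yet started. Hold the sizes only in a restricted randomization document kept by the database group, and take the size out of the site-facing protocol. At an assumed 12 women per site, the certain share falls to about 3% with 3, 6 and 9, or 5% to 6% with 6 and 9.

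Reconcile 6.9.2 with 6.9.5 on whether the Site PI knows assignments, and state which site roles may see them before the next woman is randomized.

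The cost is a short amendment, which Section 14.3 requires DCP and the IRB to approve before use, a new list for the unstarted blocks, and slightly looser 2:1 balance within a site. The sample size and the analysis do not change.

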### **13.3 Accrual and Feasibility**

We plan to consent and screen 108 potentially eligible subjects in the study over 2.5 years at four clinical centers. Our goal is to randomize 48 participants. The randomized participants will receive the intervention for approx. 4 weeks; and will be followed up for an additional approx. 3-6 months period. They will be followed closely to monitor the toxicity and drug compliance.

### **13.4 Primary Objective, Endpoint, Analysis Plan**

The primary objective of this study is to evaluate the effect of the nelipecimut-S vaccine on nelipecimut-S-specific CTL measured in blood in DCIS participants that are HLA-A2 positive. We will use a dextramer assay, which is a flow cytometry based assay, to enumerate the number of nelipecimut-S-specific CTL generated in response to vaccination with the nelipecimut-S peptide. The number of nelipecimut-S-CTL will be determined in participants at the following time points: pre-vaccination, at the time of surgery (after two preoperative vaccinations), 1 month (+/- 7 days) after surgery, and 3-6 months after surgery at the time of the final study visit. The change in the number of nelipecimut-S-CTL for an individual participant between the pre-vaccination timepoint and the 1 month (+/- 7 days) after surgery timepoint will be used as the primary endpoint measure for this study.

At the end of the study, the change of nelipecimut-S-specific CTL at the 1 month (+/- 7 days) after completion of the vaccination series timepoint from baseline will be estimated for each group using mean, standard deviation, median, minimum and maximum. Two-sample t-test or Wilcoxon rank sum test, whichever appropriate, will be used to compare the change between the two groups. Nelipecimut-S-specific CTL will also be measured repeatedly through 3 months after surgery. Repeated measures analysis including mixed effects model will be performed to analyze the effect of treatment on nelipecimut-S-specific CTL change over time [35]. We will evaluate the results in the whole participant population as well as the participants with or without radiation treatment separately, when appropriate

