At the time of the initial planned analysis of the combined results of the two concurrent neli pepimut-S +GM-CSF phase II trials in node-positive and node-negative disease-free breast cancer participants described above [12, 13], a total of 171 participants were enrolled; 90 participants received the neli pepimut-S vaccine while 81 were in the observation arm [13]. Toxicity was minimal with local reactions being grade 1 (in 81% of participants) and grade 2 (19%). Systemic toxicity was grade 0 (12%), 1 (71%), 2 (14%), and 3 (2%) (Figure 1). The most common systemic toxicities were bone pain, flu-like

symptoms and fatigue which are attributable to the GM-CSF. There were no grade 4 or 5 toxicities. All participants demonstrated *in vitro* immunologic responses and *in vivo* delayed type hypersensitivity (DTH) responses post-vaccination. With respect to *in vitro* immune responses, they were assessed using a dimer assay which enumerates the number of epitope-specific CTL (i.e. nelipepimut-S-CTL). A recurring pattern of clonal expansion was observed among vaccinated participants with an increasing percentage of CD8+ nelipepimut-S-CTL with successive vaccinations that peak during the vaccination series and then contract and plateau by the completion of the series. The peak clonal expansion most commonly occurred after the third inoculation [12, 13]. At a median follow-up of 20 months, the recurrence rate seen in the vaccinated participants was 6% compared to 15% for participants in the observation group ( $p=0.04$ ). The level of nelipepimut-S-specific CTL generated in response to vaccination was assessed in HLA-A2+ participants enrolled on the study and 35% of participants were found to have a nelipepimut-S-CTL level above the mean with the recurrence rate among those participants being 3%. For participants with a nelipepimut-S-CTL level below the mean, the recurrence rate was 14% [20].

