## 9. CORRELATIVE/SPECIAL STUDIES

### 9.1 Rationale for Methodology Selection

#### 9.1.1 Enumeration of nelipepimut-S-specific CTL

**Rationale.** MHC class I vaccines such as nelipepimut-S+GM-CSF are designed to stimulate clonal expansion of antigen-specific CTL. In a subset of 86 patients from our phase I/II trials investigating nelipepimut-S+GM-CSF, we used a dimer assay to quantify nelipepimut-S-specific CTL and found that only 1 of 30 (3%) patients with -specific CTL levels above the mean recurred compared to 8 of 56 (14%) with levels below the mean [21]. This suggests that robust *in vitro* immunologic responses may identify participants in whom vaccination will be efficacious. The primary objective of this trial is to evaluate the nelipepimut-S-specific CTL response in participants receiving NeuVax versus control participants receiving GM-CSF alone.

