## **13. STATISTICAL CONSIDERATIONS**

### **13.1 Study Design/Description**

This is a Phase II, randomized, single-blind study with 2 intervention arms. A total of 108 DCIS participants will be consented and screened for eligibility and, with a conservative estimate, 48 (45%) participants are expected to be HLA-A2 positive. These 48 participants will be randomized 2:1 to vaccine and GM-CSF alone groups. Accounting for 10% attrition rate while on study and for approx. 5% non-evaluable sample rate, we expect to have 40 evaluable participants, 27 in vaccine and 13 in GM-CSF alone group, that have all baseline, post-vaccination (pre-surgery), and post-surgery measures of nelipepimut-S-specific CTL. With 27 and 13 in vaccine and GM-CSF alone groups, respectively, we will have 82% power to detect an effect size of 1 on the change of nelipepimut-S-specific CTL ("1 month (+/- 7 days) after completion of the vaccination series timepoint" minus pre-1st vaccine) between the two groups, corresponding to change of  $0.05\% \pm 0.05\%$  in vaccine group and  $0 \pm 0.05\%$  in control group, using two-sided t-test with a significance level of 0.05.

The decision rule for declaring the agent promising will be if we detect an effect size of 1 on the change of nelipepimut-S-specific CTL, and if there are not greater than 10% grade III AEs attributed to the active

study drug or IV AEs of any attribution. Completion of the current study will provide the necessary data to determine the next phase of study, specifically whether a subsequent, larger phase II will be conducted versus a phase III study.

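### The primary CTL test is valid, but it uses baseline only by subtraction and omits the site stratum; a baseline- and site-adjusted model on a prespecified scale would depend less on chance imbalance

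*Combined protocol and SAP*

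**What the plan says.** Section 13.4 defines the primary endpoint as each participant's change in CTL from before vaccination to 1 month after surgery, then states: "Two-sample t-test or Wilcoxon rank sum test, whichever appropriate, will be used to compare the change between the two groups". No rule for choosing between the two tests is given, and no scale is named. The same section adds a mixed model over time, but names no covariates for it and does not make it primary.

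Section 13.2 says: "We will stratify the randomization by site using random permuted block design with the block size of 6". Section 13.3 plans accrual "over 2.5 years at four clinical centers". No analysis names site or baseline CTL as a term.

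Section 13.1 claims 82% power for an effect size of 1 on the change (0.05% against 0, SD 0.05% in each arm) with 27 and 13 evaluable participants, described as those "that have all baseline, post-vaccination (pre-surgery), and post-surgery measures of nelipepimut-S-specific CTL". It also ties the go/no-go decision to that quantity: "The decision rule for declaring the agent promising will be if we detect an effect size of 1".

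Section 6.9 says: "The Statistician, Site Study Pharmacist and other investigators will not be blinded".

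On the shape of CTL data, section 9.1.1 reports recurrence in 1 of 30 earlier-trial patients with CTL above the mean, "compared to 8 of 56 (14%) with levels below the mean". Section 2.3 says of the same programme: "35% of participants were found to have a nelipepimut-S-CTL level above the mean".

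**The concern.** A change score is fully efficient only if a one-unit difference at baseline predicts a one-unit difference at follow-up. If the slope is lower or higher, part of any chance baseline difference between the arms stays in the estimated effect. With 13 controls such differences will not be small. The estimate also feeds a decision rule set at an effect size of 1, so luck at baseline bears on whether the agent is called promising.

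The baseline sample is already collected, and the randomisation is already stratified by site, so the information needed for adjustment exists. If CTL is right-skewed, as the earlier trials suggest, the scale of the adjusted model matters as much as the adjustment itself.

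**Working it through.** **1. The plan's own figure.** From 13.1: effect 0.05/0.05 = 1, n = 27 and 13, two-sided 0.05, 38 df. Noncentrality = √(27×13/40) = 2.96. The noncentral t gives 82.3%, matching the stated 82%.

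**2. Baseline imbalance.** The SE of the baseline difference is √(1/27 + 1/13) = 0.338 baseline SD. Let ρ be the baseline/follow-up correlation and k the ratio of follow-up SD to baseline SD. Neither is in the documents, so both are assumed over a range. The slope is ρk. Given a baseline difference D, the expected change-score difference is the true effect plus (ρk − 1)D. In units of the SD of change, a 1-SE imbalance shifts the estimate by 0.338(ρk − 1)/√(1 + k² − 2ρk). At k = 1 the shift is 20, 17, 13 and 7.5% of the target effect for ρ = 0.3, 0.5, 0.7 and 0.9, opposite in sign to the imbalance. At k = 2, ρ = 0.5 (slope 1) it is zero.

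**3. Power of the adjusted model, normal data.** The residual SD relative to the SD of change is k√(1 − ρ²)/√(1 + k² − 2ρk). At k = 1 this is √((1 + ρ)/2) = 0.81, 0.87, 0.92 and 0.97. By formula on 34 df (38 less one for baseline and three for site), power is 94.6, 91.3, 87.7 and 84.0%. Simulation also counts the cost of chance correlation between arm and covariates, and gives (%):

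| k | ρ 0.3 | ρ 0.5 | ρ 0.7 | ρ 0.9 |
|---|---|---|---|---|
| 1 | 94.1 | 90.2 | 86.3 | 82.4 |
| 1.5 | 85.6 | 82.0 | 80.7 | not run |
| 2 | 82.0 | 80.9 | 83.1 | not run |
| 3 | 80.9 | 81.7 | 88.4 | not run |

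The comparator is 82.3%. The largest gain is 94.1 − 82.3 = 11.8 points. The losses, about 1.5 to 2 points, fall where ρk is near 1.

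**4. Skew.** 30 of 86 earlier CTL levels (34.9%; exact 95% CI 24.9 to 45.9%) lay above the mean (two-sided sign test against 50%, p = 0.007). If the shape is lognormal, P(above mean) = 1 − Φ(s/2), so the log-SD s is 0.78 (0.20 to 1.35). With the effect tuned so that the Wilcoxon test has about 82% power at s = 0.78, raw-scale adjustment has only 60 to 72%, a loss of roughly 10 to 23 points.

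**5. Scale set by a rule.** Rule tested: log scale if the skewness of the pooled pre-vaccination values exceeds 1, otherwise raw. The fold effect varies between people (log-SD 0.5, assumed). The comparator is the planned t-test or Wilcoxon test chosen by the same rule. Power (%), ρ = 0.3/0.5/0.7/0.9:

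| log-SD | Adjusted | Planned tests |
|---|---|---|
| 0.78 | 86.3/84.0/82.2/80.6 | 80.4/80.7/80.8/80.8 |
| 0.5 | 82.6/80.0/76.9/74.9 | 80.3/80.7/80.0/80.1 |

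The differences run from +5.9 to −0.2 points at log-SD 0.78 and from +2.3 to −5.2 points at 0.5. Type I error under the rule was 4.6 to 5.3% in every setting run.

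**6. Site.** A site effect on CTL level cancels in the change (t-test type I error 5.2%). If site affects the change itself (SD 0.03%, assumed), the unadjusted t-test becomes conservative at 3.6%, against 5.0% for the adjusted model.

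**The case against.** The strongest reply is that nothing here is an error and that the gain is uncertain. Much of that stands.

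- Section 2.3 reports clonal expansion after vaccination, so k above 1 is plausible. Six of the nine cells with k above 1 are at or below 82.3% (two of them, at 82.0, are effectively ties).
- Against a test simply fixed as Wilcoxon (about 82%), the rule-based model at log-SD 0.78 gains about 4 points at ρ = 0.3 and loses about 1 at ρ = 0.9.
- The skew evidence is indirect. It comes from a dimer assay rather than this trial's dextramer, concerns levels rather than change, and comes from trials that mixed doses and schedules.
- A scale rule with loose cut-offs would add ambiguity. The cut-off and the log offset must therefore be written down as numbers.
- Thirteen controls over four sites is about three per site, and blocking already limits site imbalance.

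The planned mixed model could carry the adjustment, but with no covariates named and no primary status it does not do so as written.

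A reader might infer more than the documents support:

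- *That the planned test is biased or the trial underpowered.* Randomisation makes baseline imbalance part of ordinary sampling error, already counted in the 5% level and the 82%.
- *That leaving out site biases the result.* It does not; at most it is slightly conservative.
- *That the open choice of test will be used to pick the smaller p-value.* Doing so could raise type I error to as much as 7% in the settings run, but nothing in the plan says it would be done.

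**Conclusion.** The point holds as a recommended improvement, not as a defect in validity or sample size. The benefit that does not rest on an optimistic assumption is an estimate that depends less on a pre-treatment difference between arms. In simulation at k = 1 and ρ = 0.3, 0.5 and 0.7, the change-score estimate correlated with baseline imbalance at −0.59, −0.50 and −0.38; the adjusted estimate correlated at about zero.

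The effect on power is conditional: about +12 to −2 points under normal data, about +6 to 0 at log-SD 0.78 and about +2 to −5 at log-SD 0.5. These ranges rest on assumed ρ, k, distribution and response pattern. No power gain is claimed for site; including it makes the analysis match the randomisation and corrects a slightly conservative standard error. Raw-scale adjustment alone would be a poor substitute for the Wilcoxon option if CTL is skewed. Confidence is medium.

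**What to change.** In 13.4:

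1. Make the primary analysis a linear model of CTL at 1 month after surgery on arm, baseline CTL and site, two-sided 0.05, reporting the adjusted effect (a difference, or a ratio on the log scale) with its 95% CI. State a fixed rule for pooling small sites.
2. Fix one scale before any post-vaccination data are seen, using only pooled pre-vaccination values, which cannot depend on arm; this matters because the statistician is unblinded. Use raw if roughly symmetric and log with a stated offset if skewed. Give the skewness cut-off as a number (the calculations used 1). The documents state no detection limit, so the offset must be given explicitly.
3. Keep the unadjusted t-test or Wilcoxon test on change as the supporting analysis, with the choice tied to the same scale rule.
4. Name baseline CTL and site as terms in the repeated-measures model.

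In 13.1, add one sentence: for the decision rule, report the raw-scale difference divided by the pooled SD of change, whichever scale the test uses. Sections 13.1 and 13.4 also place the endpoint 1 month after the vaccination series; reconcile this with 1 month after surgery when editing.

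Cost: SAP wording and 4 of 38 degrees of freedom. There are no new data or participants, and no one is lost, since a participant without a baseline value has no change score either. The power risk is the lower end of the ranges above.
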